7.9.3 Main Efficacy Outcomes

Neurocognitive Composite

A composite neurocognitive score will be generated based on performance on objective measures. The composite index score will be computed in two ways. The first will be an average of measures evaluating working memory (SB-5 working memory subscale), processing speed (CPT-3 mean reaction time), and fine motor skills (Purdue Pegboard Test-average of both hands). The second will include the above average weighted by two-thirds and an average of the remaining standardized, norm-referenced neurocognitive measures (e.g., non-verbal ability, visuomotor skills, verbal learning, receptive and expressive language) weighted by one-third. The first method will be preferred if nearly complete data is observed on the 3 primary constructs (working memory, processing speed, and fine motor skills) in randomized patients. The second will be preferred if missing data is present on >20% of randomized patients. In order for any patient to be included in the study they must complete measures from at least one of the three primary efficacy constructs. If patients cannot complete the full Stanford Binet, the Mullen Scales of Early Learning may be substituted. In a similar

fashion, if the CPT-3 cannot be completed, the processing speed index of the Wechsler scales may be substituted as an alternative measure of processing speed.

Measures were chosen based on previous empirical findings in a cross-sectional cohort study of PTEN patients with ASD. In this study, measures of working memory and processing speed were differentially impaired relative to other cognitive measures, including IQ. Furthermore, the cognitive deficits seen in these patients were related to reduced PTEN protein levels and brain white matter abnormalities. Specifically, in a cross-sectional mediational model, reduced PTEN protein levels led to greater brain white matter abnormalities which, in turn, led to greater cognitive difficulties. Although not evaluated using standardized testing, in our prior cohort of PTEN patients with ASD, every patient had a history of fine motor difficulties, occupational therapy, and/or observations during testing of significant fine motor weaknesses. Motor difficulties are also consistent with brain white matter abnormalities. Thus, the neurocognitive index will include measures that have both empirical and biological bases for inclusion as outcome measures.

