In the second version of the neurocognitive composite, the primary justifications for including the remaining neurocognitive measures are: 1) if significant missing data is seen on measure of processing speed, working memory, and fine motor skills, including a minor component of additional neurocognitive measures will ensure more reliably obtained data is contributing to the measurement of change, and 2) PTEN expresses in all of the cells of the body, the brains of PTEN patients showed widespread changes that included white matter abnormalities but also regional gray matter changes, and mouse models of PTEN loss have suggested that dendrite and synaptic dysfunction is also a consequence. Thus, it is reasonable to expect a range of neurocognitive functions might improve. Inclusion of other neurocognitive measures as the minority part of the index will ensure that improvements in other domains, such as expressive language, also have an opportunity to contribute to individual patient outcome measurements. Given that we do not yet know with certainty which neurocognitive functions are most likely to improve in this whole brain condition, allowing for possible improvement in other domains seems prudent.

Use of a neurocognitive composite score has several advantages. Assuming that everolimus treatment does not impair some functions while improving others (an unlikely scenario), a composite score is likely to be highly reliable, can be computed in all patients even if 1 or 2 measurements are missing or could not be completed, and has good domain coverage to capture possible variability across patients in the specific neurocognitive domains showing improvement. An example of the latter advantage, is if some individuals show improvements in processing speed while others show improvements in working memory. The neurocognitive composite would identify improvements in both of these sets of patients. As such, the neurocognitive composite may be more sensitive to change than any individual measure. Furthermore, a composite primary efficacy outcome will not require additional multiple comparison correction.

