7.13 Safety Outcomes

The Dosage Record and Treatment Emergent Symptom Scale (DOTES): This is a general rating scale published by the Early Clinical Drug Evaluation Unit of the National Institute of Mental Health. The scale has been widely used clinically for both children and adults to assess many central nervous system side effects as well as some behavioral side effects. It will be completed at screening, baseline, and at each subsequent visit. In addition, patients will be interviewed using the C-SSRS to proactively assess patients for suicidality and mood disturbances. If the patient's and/or parents' responses are of concern, the investigator performing the interview may refer them to a mental health professional at the hospital. More detailed information about the C-SSRS can be found in section 4.6.5. Specific adverse events will also be classified and graded according to Common Terminology Criteria for Adverse Events (CTCAE) v5.0. Use of CTCAE will allow direct comparison with past and current clinical trials with everolimus, including the neurocognitive trial described in previous sections (NCT01289912). Vital signs (blood pressure, pulse, and temperature), height and weight will be obtained during screening, baseline, and at each subsequent visit.

Table 12. Primary and Secondary Efficacy and Safety Outcome Measures.

	Domain	Measure							
Primary Efficacy Outcome	Neurocognitive Composite	Average working memory (SB-5 working memory), processing speed (CPT mean reaction time) and fine motor (Purdue Pegboard-average of both hands) subtests weighted at 2/3 of the composite score and the average of all other available neurocognitive testing measures (receptive and expressive language, non-verbal ability, verbal learning, sustained attention, impulsivity, and visuomotor skills) weighted 1/3 of the score.							
	Global Ability	Stanford-Binet-5 (SB-5): Full scale IQ, Verbal IQ, and Non-Verbal IQ or the Mullen Scales of Learning: Cognitive IQ							
	Attention	Conners' Continuous Performance Test -3 (CPT-3/K-CPT-2): Discriminability (d') and Omissions							
	Processing Speed	Conners' Continuous Performance Test -3 (CPT-3/K-CPT-2): Mean Reaction Time; in cases where an individual cannot complete the CPT we will administer the appropriate Wechsler processing speed index subtest.							
	Impulsivity	Conners' Continuous Performance Test (CPT): Commissions and Bias							
	Long-Term Memory	WRAML-2 Verbal Learning: Scaled score							

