CGI Scale: Severity & Improvement	IE	Efficacy	X ³ **	X**	X ⁴	X**	X ⁴	X ⁴	X**		
Vital Signs	Clinician	Safety		Χ		x			Х		
Physical / Neurological Exam	Clinician	Safety							X**		х

³At the baseline visit, only the CGI: Severity scale will be completed.

⁴PTEN-associated protein blood collections will be collected at either the screening or baseline visit (as well as at the 3 month and 6 month visits)

⁵CGI optional for phone interviews month 2, month 4, and month 5.

^{*=} May be performed by phone or in person

^{**=} May be performed by phone/videoconference under extenuating circumstances (note: Physical / Neurological Exam can not be completed in full remotely, but a modified version can be performed)

Dermoscopy	Clinician	Efficacy				X**			X**		
Microbiome/	Jiiiilolaii	Lindacy				^					
Mycobiome Sample Collection		Efficacy				х			x		
Tanner Staging	Clinician	Safety							Х		
Side-effects (CTCAE v5.0 + DOTES)	Clinician	Safety	#	X**	х	X**	х	х	X**	х	
Columbia-Suicide Severity Rating Scale	Clinician	Safety		X**		X**			X**		
Laboratory tests ¹	Lab	Safety	#	Х		Х			Х		Х
Everolimus level (only done after M1 if needed)	Lab	Dose Adjust		х							Х
PTEN-associated proteins	Lab	Efficacy				Х			X	,	
Concomitant treatment log	Clinician	Safety+ Efficacy	#	Х	Х	Х	х	Х	X	Х	
Primary Efficacy Outcome Neurocognitive Composite	Clinician	Efficacy	#			х	O		х	х	
Conners' Continuous Performance Test (CPT-3/K-CPT-2)	Clinician	Efficacy				x			x		
Stanford-Binet Fifth Edition (SB- 5) / Mullen Scales of Early Learning (MSEL)	Clinician	Efficacy							х		
Stanford-Binet Working Memory Subscale Only	Clinician	Efficacy				Х					
Purdue Pegboard (PP)	Clinician	Efficacy				Х			Х		
Wechsler Processing Speed Index	Clinician		30			Х			Х		
Wide Range Assessment of Memory and Learning-2 (WRAML-2)	Clinician	Efficacy				X**			X**		
Peabody Picture Vocabulary Test – Fourth Edition (PPVT-4)	Clinician	Efficacy				X**			X**		
Expressive Vocabulary Test – Second Edition (EVT-2)	Clinician	Efficacy				X**			X**		
Autism Diagnostic Observation Schedule (ADOS-2)	Clinician	Efficacy							х		
Social Responsiveness Scale – Second Edition (SRS-2)	Parent Report	Efficacy				Х			Х		
Repetitive Behavior Scale – Revised (RBS-R)	Parent Report	Efficacy				Х			Х		

Developmental Coordination Disorder Questionnaire (DCDQ)	Parent Report	Efficacy		Х		X	х	
Behavior Rating Inventory of Executive Function (BRIEF)	Parent Report	Efficacy		Х		X		
Adult/Child Behavior Checklist	Parent Report	Efficacy		X		X	X	

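### Nothing in the plan keeps a patient's neurocognitive composite on the same tests and instruments from baseline to follow-up, so a change in test mix can appear as a change in the patient

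*Combined protocol and SAP*

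**What the plan says.** - **First composite** (section 7.9.3): "The first will be an average of measures evaluating working memory (SB-5 working memory subscale), processing speed (CPT-3 mean reaction time), and fine motor skills".
- **Second composite:** two thirds of that core average plus one third of what Table 12 (section 7.13) calls "the average of all other available neurocognitive testing measures". Section 7.9.3 prefers this version if more than 20% of randomized patients have missing data.
- **Missing tests** (section 7.9.3, repeated in section 3.5): the composite "can be computed in all patients even if 1 or 2 measurements are missing or could not be completed". The only minimum is for entry, where patients are told of as follows: "they must complete measures from at least one of the three primary efficacy constructs". No minimum is set per visit.
- **Substitution** (section 7.9.3): "If patients cannot complete the full Stanford Binet, the Mullen Scales of Early Learning may be substituted"; and "if the CPT-3 cannot be completed, the processing speed index of the Wechsler scales may be substituted".
- **Schedule** (Table 11): the full SB-5 or Mullen is given at screening and Month 6. Baseline and Month 3 have the working-memory subscale only. Section 7.9.4 names SB-5 or Mullen as the source of non-verbal ability, which belongs to the second composite.
- **Remote visits:** section 4.3 lets Months 1, 3 and 6 be held by phone or video. In Table 13A, among the cognitive tests, only WRAML-2, PPVT-4 and EVT-2 carry the mark explained as "May be performed by phone/videoconference under extenuating circumstances". CPT-3, SB-5 and Pegboard do not carry it, and neither does the composite row.
- **Missing data in the model** (section 17): data points lost through attrition are assumed missing at random. Missing components are not mentioned.

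**The concern.** A composite measures change only if it is the same composite at both ends. Here a patient could have three core tests at baseline and two at Month 6, or CPT-3 at one visit and Wechsler at another. The tests differ in level, so the average moves even when the patient does not.

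The mixed model cannot repair this. It sees one number per visit, and a number built from two tests looks as complete as one built from three. Moving to the second composite does not help either, because two thirds of it is the same core average with the same gap in its rules.

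At stake is the main efficacy endpoint. Under section 17.1, nominal one-sided significance on it makes it a candidate for Phase III evaluation, and there are only 20 patients per arm.

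**Working it through.** **1. The plan's own power figures** (section 17.1: 20 per arm, one-sided alpha 0.05). A two-sample noncentral-t calculation gives 0.799 at 0.80 SD (stated 0.80) and 0.646 at 0.65 SD (stated 0.65). The stated 0.83 at 0.50 SD with r = .30 is reproduced as 0.827 by a group-by-time F test with f = 0.25, noncentrality 0.25² × 40 × 3 / 0.7 = 10.7, and 2 and 76 df. These figures presume a composite measured the same way at each visit.

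**2. Unit.** Section 17.1 equates 0.65 SD with 10 standard-score points. Since 0.65 × 15 = 9.75, 1 SD is about 15 points.

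**3. One patient, first composite.** Let the lost test lie g below the mean m of the other two.
- With all three tests: (2m + m − g)/3 = m − g/3.
- With the other two only: m.
- Shift: +g/3. For an assumed g of 0.5 SD it is 0.17 SD (2.5 points); for 1 SD it is 0.33 SD (5 points).
- If the lost test lies g above the others, the shift is −g/3.

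**4. One patient, second composite.** The core average has weight 2/3, so the same loss shifts it by 2g/9: 0.11 to 0.22 SD.

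**5. Schedule effect on the second composite.** Table 12 lists seven other domains. With one measure per domain, adding non-verbal ability at Month 6 when it is h away from the other six moves that block by h/7 and the composite by h/21, which is under 0.05 SD for h = 1 SD. The scheduled change is the same for both arms.

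**6. Arm level.** The mean shift is g/3 times the difference in loss rates. For an assumed 20-point difference: 0.20 × 0.17 = 0.03 SD and 0.20 × 0.33 = 0.07 SD.

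**7. Simulation.** ANCOVA, 20 per arm, 6,000 runs per scenario. Assumptions, none of them in the documents: test means at 0, −7.5 and −15 points, between-test correlation 0.4, retest correlation 0.8, complete baseline. The weakest test then has g = 11.25, so its loss gives a shift of 3.75 points.

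| Loss, everolimus vs placebo | True effect | Bias (points) | One-sided rejection rate |
|---|---|---|---|
| Weakest test, 20% vs 20% | 0 | 0.0 | 0.049 |
| Weakest test, 20% vs 5% | 0 | 0.6 | 0.085 |
| Weakest test, 30% vs 10% | 0 | 0.7 | 0.107 |
| Weakest test, 30% vs 0% | 0 | 1.1 | 0.134 |
| Weakest test, 40% vs 10% | 0 | 1.1 | 0.134 |
| None | 5 points | 0.0 | 0.888 |
| Random test, 20% vs 20% | 5 points | about 0 | 0.839 |
| Weakest test, 30% vs 30% | 5 points | about 0 | 0.797 |

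When the lost test was random, null rejection stayed at 0.046 to 0.051 even with unequal loss rates. For a single patient with no true change, losing the weakest test raised the chance of an apparent gain of 10 points or more from 3.4% to 19.5%.

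**8. After the fix.** If the same tests and instruments enter both scores, the level shift is zero by construction.

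**The case against.** The strongest reply is that the sentence about missing measurements is part of a rationale, not a scoring rule. Substitution is worded by patient, so someone given one instrument throughout has no shift. Section 7.9 has testers attempt and re-administer every measure. Efficacy is a secondary objective in a study that section 17 calls exploratory. All of this is fair. It makes the problem less frequent, but none of it supplies a rule.

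Several stronger readings are tempting, and the documents do not support them:

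- **That the plan prescribes averaging over whatever is present at each visit.** This is an inference. The text only fails to prevent it.
- **That losing a core test always raises the score.** Section 7.9.3 reports that "measures of working memory and processing speed were differentially impaired relative to other cognitive measures, including IQ". That compares two core constructs with non-core tests and does not rank the core tests among themselves. It also says fine motor skill had not been evaluated with standardized testing.
- **That a remote Month 6 visit would be scored on language and verbal learning alone.** That would move the second composite by two thirds of the gap between blocks, or 0.33 to 0.67 SD for an assumed gap of 0.5 to 1 SD. But the composite row in Table 13A has no remote mark, all three core tests would be absent rather than one or two, and no text lets the one-third block stand alone. The natural reading is a missing composite.
- **That a shift of 0.17 to 0.33 SD can be set against the 0.65 SD of interest.** The first is one patient's shift; the second is a contrast between arms.

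**Conclusion.** The gap is real and should be closed, at moderate weight. Following the plan as written can give a noisier change score, and a biased one if loss of a weak or strong test differs by arm.

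The per-patient size is g/3, or 0.17 to 0.33 SD for an assumed g of 0.5 to 1 SD, in either direction. At arm level it is about 0.03 to 0.07 SD for an assumed 20-point difference in loss rates. In the simulated scenarios with more loss of the weakest test on everolimus, one-sided type I error was 0.085 to 0.134. With loss in both arms, power for a 5-point effect fell from about 0.89 to between 0.80 and 0.84.

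The documents give neither the gaps between tests nor any expected loss rates, by arm or overall, so these figures are ranges and not forecasts. The stated power figures are not contradicted by this point.

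**What to change.** Add to the SAP:

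1. Score each follow-up composite and its baseline comparator only from tests done with the same instrument at both visits. Fix the instrument for each construct, per patient, by what was completed at baseline.
2. State that the screening SB-5 serves as baseline for non-verbal ability, or leave that measure out of the second composite.
3. Set the composite to missing when no core test is available. This covers remote Month 3 and Month 6 visits.
4. Add a component-level mixed model, with component-by-visit terms and patient random effects, as a sensitivity analysis. It should not be the main analysis, because a common treatment effect across components would drop the two-thirds/one-third weighting and so change the endpoint.

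A rule that moves a patient to Wechsler at all visits whenever CPT-3 is missing at any visit is best avoided: it lets events after randomization choose the instrument.

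Two texts also need reconciling. Table 13A's footnotes give the double asterisk two meanings (remote conduct, and primary outcome only). Section 4.3 both allows remote Month 3 and 6 visits and says that missed on-site visits warrant termination.

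Cost: some observed component scores are not used in the main composite, and there is slightly more analysis work. The baseline comparator may differ between Month 3 and Month 6, so the SAP must say how it enters the growth-curve model. No new data are needed. The rule removes the level shift, but not any selection in who completes which test.

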7.9.4 Additional Secondary Efficacy Outcomes

Attention Improvement

Conners' Continuous Performance Test, Third Edition (CPT-3/K-CPT-2): Discriminability index (d') and Omissions

Processing Speed Improvement

Conners' Continuous Performance Test, Third Edition (CPT-3/K-CPT-2): Mean Reaction Time Weschler Processing Speed Index Subtests: Processing speed if CPT cannot be administered

Impulsivity Improvement

Conners' Continuous Performance Test, Third Edition (CPT-3/K-CPT-2): Commissions and Bias (B')

Working Memory Improvement

Stanford-Binet Intelligence Scales, Fifth Edition (SB-5) Working Memory: Standard Score

Global Clinical Improvement

Clinical Global Improvement Scale; Severity and Improvement subscales

Improving Global Cognitive Ability

Stanford-Binet Intelligence Scales, Fifth Edition (SB-5) or Mullen Scales of Early Learning; Full scale, verbal and nonverbal ability (IQ)

Version Date: 05Feb20

Improving Long-Term Memory

Wide Range Assessment of Memory and Learning, Second Edition (WRAML-2) – Verbal Learning: Scaled Score

Improving Language

Peabody Picture Vocabulary Test (PPVT-4): Standard Score Expressive Vocabulary Test Second Edition (EVT-2): Standard Score

Improving Motor Deficits

Purdue Pegboard (Pegs): Dominant and non-dominant hand combined standard scores Developmental Coordination Disorder Questionnaire (DCDQ): Total score

Targeting Autism Symptoms

Autism Diagnostic Observation Schedule (ADOS): Calibrated severity scores

An interviewer-based, semi-structured observational schedule for the assessment of individuals with possible autism spectrum disorders. The ADOS is widely regarded as an excellent phenotyping and diagnostic aid, and is used in many large-scale autism studies throughout the world, including the AGRE (Autism Genetic Resource Exchange www.agre.org) and IMGSAC (International Molecular Genetics Study of Autism Consortium www.well.ox.ac.uk/monaco/autism/IMGSAC.shtml) studies.

Autism Diagnostic Interview - Revised (ADI-R): Item scores (ever/most abnormal)/ current

For children with mental age <18 months, clinical judgment should be used when determining the reliability/validity of an ADI-R administration. The ADI-R is a semi-structured diagnostic parent interview that probes for current behaviors and a developmental history consistent with autism symptomology. The ADI-R contains questions about an individual's early development, communication, social interaction and patterns of behavior.

Social Responsiveness Scale, Second Edition (SRS-2): Total T-score

Repetitive Behavior Scale - Revised (RBS-R): Total raw score

Improving Associated Behaviors

Behavior Rating Inventory of Executive Function (BRIEF): General executive composite and sub-scale scores Adult/Child Behavior Checklist (CBCL ARF/CBCL): Total problems T score Short Sensory Profile (SSP): Total Score

Improving Adaptive Behaviors

Vineland Adaptive Behavior Scales-III (VABS-III) Caregiver report: Composite and scale scores.

A measure of functional adaptive behavior, i.e. ability to cope with personal and social skills in everyday life that may be deficient in autism or developmental delays. Tester completes a questionnaire through interview with parent or caregiver. Any age. No parallel forms. Outcome measures: raw scores converted to scaled scores, then a summary value for a number of domains.

Table 11 Neuropsychological Assessments Timeline

Instrument	Information Source	Screening (Visit 1)	Baseline^ (Visit 2)	3-month [#] (Visit 5)	6-month [#] (Visit 8)
Primary Efficacy Outcome Neurocognitive Composite	Testing		Х	Х	Х
Stanford-Binet Fifth Edition (SB-5) / Mullen Scales of Early Learning (MSEL)	Testing	Х			х
Columbia-Suicide Severity Rating Scale	Interview	Χ		X	X
Stanford-Binet Working Memory Subscale Only	Testing		Х	X	
Conners' Continuous Performance Test (CPT-3/K-CPT-2)	Testing	X	х	x	x
Wechsler Processing Speed Index (PSI)	Testing		X	X	X
Wide Range Assessment of Memory and	Testing		Х	X	X

Learning-2 (WRAML-2)					
Peabody Picture Vocabulary Test – Fourth	Testing		X	X	x
Edition (PPVT-4)			^	^	^
Expressive Vocabulary Test – Second	Testing		X	X	x
Edition (EVT-2)					
Purdue Pegboard (PP)	Testing	Χ	X	X	X
Autism Diagnostic Observation Schedule (ADOS-2)	Observational		Х		X
Social Responsiveness Scale – Second	Parent/Caregiv				
Edition (SRS-2)	er/Informant or		X	X	X
	Self- Report				
Repetitive Behavior Scale – Revised (RBS-	Parent/Caregiv				
R)	er/Informant or		X	X	X
	Self Report				
Developmental Coordination Disorder	Parent/Caregiv				
Questionnaire (DCDQ)	er/Informant or		X	X	X
	Self Report				
Behavior Rating Inventory of Executive	Parent/Caregiv				
Function (BRIEF)	er/Informant or		X	X	X
	Self Report				
Adult/Child Behavior Checklist (CBCL	Parent/Caregiv				
ARF/CBCL)	er/Informant or		X	X	X
	Self Report				
Short Sensory Profile (SSP)	Parent/Caregiv				
	er/Informant or		X	X	X
	Self Report				
Vineland Adaptive Behavior Scales (VABS-	D 110				
III) – caregiver report	Parent/Caregiv		X	X	X
	er/Informant or				
Autions Disposatio Interview (ADLD)	Self Report				
Autism Diagnostic Interview (ADI-R)	Direct Interview				
	with		X		
	Parent/Caregiv				
	er/Informant				

Note: Individuals who are participating in the longitudinal study: Natural History of Individuals with Autism and Germline Heterozygous PTEN Mutations can leverage measures completed within +/- 6 month for this study at the discretion of the study psychologist.

